**Table 8 Imaging and Treatment After First Radiologic Evidence of Progressive Disease**

[figure not shown]
	Clinically Stable		Clinically Unstable	
	Imaging	Treatment	Imaging	Treatment
First radiologic evidence of disease progression by RECIST 1.1 per investigator assessment	
[For those studies in which PFS is the primary endpoint, add this: Submit the imaging to BICR for verification]
 
Repeat imaging at 4 to 8 weeks to confirm disease progression
	May continue study treatment at the assessment of the investigator and after the participant's consent	
[For those studies in which PFS is the primary endpoint, add this: Submit the imaging to BICR for verification]
 
Repeat imaging at 4 to 8 weeks to confirm disease progression per investigator's discretion only.
	Discontinue treatment
First radiologic evidence of disease progression by RECIST 1.1	Repeat imaging at 4 to 8 weeks to confirm disease progression.	May continue study intervention at the investigator's discretion while awaiting confirmatory tumor imaging by site by iRECIST.	Repeat imaging at 4 to 8 weeks to confirm disease progression per investigator's discretion only.	Discontinue treatment
Repeat tumor imaging confirms disease progression (iCPD) by iRECIST per investigator assessment.	No additional imaging required.	Discontinue treatment (exception is possible upon consultation with Sponsor).	No additional imaging required.	Not applicable
Repeat tumor imaging shows iUPD by iRECIST per investigator assessment.	Repeat imaging at 4 to 8 weeks to confirm disease progression. May occur at next regularly scheduled imaging visit.	Continue study intervention at the investigator's discretion.	Repeat imaging at 4 to 8 weeks to confirm disease progression per investigator's discretion only.	Discontinue treatment
Repeat tumor imaging shows iSD, iPR, or iCR by iRECIST per investigator assessment.	Continue regularly scheduled imaging assessments.	Continue study intervention at the investigator's discretion.	Continue regularly scheduled imaging assessments.	May restart study intervention if condition has improved and/or clinically stable per investigator's discretion. Next tumor imaging should occur according to the regular imaging schedule.

	Clinically Stable		Clinically Unstable	
	Imaging	Treatment	Imaging	Treatment
First radiologic evidence of disease progression by RECIST 1.1 per investigator assessment	
[For those studies in which PFS is the primary endpoint, add this: Submit the imaging to BICR for verification]
 
Repeat imaging at 4 to 8 weeks to confirm disease progression
	May continue study treatment at the assessment of the investigator and after the participant's consent	
[For those studies in which PFS is the primary endpoint, add this: Submit the imaging to BICR for verification]
 
Repeat imaging at 4 to 8 weeks to confirm disease progression per investigator's discretion only.
	Discontinue treatment

iCPD=iRECIST confirmed progressive disease; iCR=iRECIST complete response; iRECIST=modified Response Evaluation Criteria in Solid Tumors 1.1 for immune-based therapeutics; iSD=iRECIST stable disease; iUPD=iRECIST unconfirmed progressive disease; RECIST 1.1=Response Evaluation Criteria in Solid Tumors 1.1; VOP=verification of progression

[For studies in which PFS is the primary endpoint, add the following: Note: If progression has been centrally verified, further management is by the site, based on iRECIST. Any further imaging should still be submitted to the iCRO, but no rapid review will occur. If RECIST 1.1 disease progression has not been centrally verified, the site should continue treatment. Whether or not treatment continues, imaging should be collected and submitted to the iCRO with VOP request until RECIST 1.1 progression is verified by BICR.]

**Figure 1: Imaging and Treatment for Clinically Stable Participants after First Radiologic Evidence of PD Assessed by the Investigator**

### 6.1.5 Tumor Tissue Collection and Correlative Studies Blood Sampling

Per SoA

### 6.1.6 Other Procedures

#### 6.1.6.1 Discontinuation and withdrawal

Participants who discontinue study intervention prior to completion of the treatment period should be encouraged to continue to be followed for all remaining study visits as outlined in the SoA and Section 6.2.

Participants who withdraw from the study should be encouraged to complete all applicable activities scheduled for the final study visit at the time of withdrawal. Any AEs that are present at the time of withdrawal should be followed in accordance with the safety requirements outlined in Section 6.2.

#### 6.1.6.2 Blinding/Unblinding: N/A

### 6.1.7 Visit Requirements

Visit requirements are outlined in Section 2.2 – Schedule of Activities. Specific procedure-related details are provided above in Section 6.1 - Trial Procedures.

### **6.1.7.1 Screening**

**6.1.7.1.1 Screening Period:** 28 days prior to the initiation of MT therapy. Patients who have been on MT therapy can proceed to PEM therapy when completing 28 days of MT therapy

**6.1.7.2 Treatment Period:** Daily oral MT therapy to follow acceptable standards of care for mitotane therapy including concomitant steroid replacement and periodic MT levels check. PEM will be given 400 mg IV on D1 (+/- 5 days) in 6 weeks cycles for total of 18 cycles.

**Post-Treatment Visits:** All patients who discontinue treatment without objective disease progression will be followed up with tumor assessment every 12 weeks ( $\pm 14$  days) or as determined by the principal investigator or designee) until disease progression or the start of a different anti-cancer therapy. Survival follow-up via phone call, medical record review, or visit with physician will occur every 3 months for 2 years once they are off-study treatment or until patient death, withdrawal of consent, patient is lost to follow-up, or study termination, whichever occurs first.

### **6.1.7.3**

#### **6.1.7.3.1 Safety Follow-Up Visit**

The mandatory Safety Follow-Up Visit should be conducted approximately 30 days after the last dose of study intervention or before the initiation of a new anti-cancer treatment, whichever comes first. Participants who are eligible for retreatment/crossover with pembrolizumab (as described in Section 5.2.2) may have up to two safety follow-up visits, one after the Initial Treatment Period and one after the Second Course Treatment.

#### **6.1.7.3.2 Efficacy Follow-up Visits**

All patients who discontinue treatment without objective disease progression will be followed up with tumor assessment every 12 weeks ( $\pm 14$  days) or as determined by the principal investigator or designee) until disease progression or the start of a different anti-cancer therapy. Survival follow-up via phone call, medical record review, or visit with physician will occur every 3 months for 2 years once they are off-study treatment or until patient death, withdrawal of consent, patient is lost to follow-up, or study termination, whichever occurs first.

#### **6.1.7.3.3 Survival Follow-up Contacts**

Participant survival follow-up status will be assessed approximately every 12 weeks to assess for survival status until death, withdrawal of consent, or the end of the study, whichever occurs first.

The first survival follow-up assessment should be scheduled as described below:

- For participants who discontinue treatment intervention and who will not enter the Efficacy Follow-up Phase, the first survival follow-up contact will be scheduled 12 weeks after the discontinuation visit and/or safety follow-up visit (whichever is last).

For participants who completed assessments in the Efficacy Follow-up Phase, the first survival follow-up contact will be scheduled 12 weeks after the last efficacy assessment follow-up visit has been performed.

#### **6.1.7.3.4 Post Study**

Participants will be required to return to clinic approximately within 30 days after the last dose of study intervention for the poststudy visit. If the poststudy visit occurs less than 14 days after the last dose of study intervention, a subsequent follow-up telephone call should be made at 30 days post the last dose of study intervention to determine if any AEs have occurred since the poststudy clinic visit.

### **6.2 Adverse Events (AEs), Serious Adverse Events (SAEs), and Other Reportable Safety Events**

The definitions of an AE or SAE, as well as the method of recording, evaluating, and assessing causality of AE and SAE and the procedures for completing and transmitting AE, SAE, and other reportable safety event reports can be found in Appendix 5.

Adverse events, SAEs, and other reportable safety events will be reported by the participant (or, when appropriate, by a caregiver, surrogate, or the participant's legally authorized representative).

The investigator and any designees are responsible for detecting, documenting, and reporting events that meet the definition of an AE or SAE as well as other reportable safety events. Investigators remain responsible for following up AEs, SAEs, and other reportable safety events for outcome.

The investigator, who is a qualified physician, will assess events that meet the definition of an AE or SAE as well as other reportable safety events with respect to seriousness, intensity/toxicity and causality. **Time Period and Frequency for Collecting AE, SAE, and Other Reportable Safety Event Information**

All AEs, SAEs, and other reportable safety events that occur after the consent form is signed but before intervention allocation/randomization must be reported by the investigator if the participant is receiving placebo run-in or other run-in treatment, if the event causes the participant to be excluded from the study, or is the result of a protocol-specified intervention, including but not limited to washout or discontinuation of usual therapy, diet, or a procedure.

- All AEs from the time of intervention allocation/randomization through 30 days following cessation of study intervention must be reported by the investigator.

- All AEs meeting serious criteria, from the time of intervention allocation/randomization through 90 days following cessation of study intervention or 30 days following cessation of study intervention if the participant initiates new anticancer therapy, whichever is earlier, must be reported by the investigator.
- All pregnancies and exposure during breastfeeding, from the time of intervention allocation/randomization through the time required to eliminate systemic exposure after cessation of study intervention as described in Section 5.11, or 30 days after cessation of study intervention if the participant initiates new anticancer therapy must be reported by the investigator. Additionally, any SAE brought to the attention of an investigator at any time outside of the time period specified above must be reported immediately to Merck if the event is considered drug-related.

Investigators are not obligated to actively seek AEs or SAEs or other reportable safety events in former study participants. However, if the investigator learns of any SAE, including a death, at any time after a participant has been discharged from the study, and he/she considers the event to be reasonably related to the study intervention or study participation, the investigator must promptly notify Merck.

All initial and follow-up AEs, SAEs, and other reportable safety events will be recorded and reported to Merck within the time frames as indicated in **Table**.

Exception: A positive pregnancy test at the time of initial screening is not a reportable event unless the participant has received study intervention.

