## 2.0 TRIAL DESIGN

### 2.1 Trial Schema

**Phase 2 trial of mitotane (MT) plus pembrolizumab (PEM) in advanced adrenocortical carcinoma (ACC)**

## 2.2 Schedule of Activities

**Table 1 Study Schedule of Activities**

	Screening	Lead-in phase	Treatment Period (cycles are 42 days) +/-5 -day window All CXD1 assessments may be performed up to 7 days before infusion					Progression	Study Completion /Early Termination Visit	Follow-Up 
Day	-28 through day -1	(Days 1-28 days $\pm$ 5)	C1 D1	C2 D1	C3 D1	C4 D1	C5D1 -last course h			
Informed consent	x									
Inclusion/exclusion criteria	x	x *								
Demographic data	x									
Pregnancy test 	x	x	x	x	x	x	x			
Physical Examination & ECOG PS 	x		x	x	x	x	x		x	
Routine labs 	x		x	x	x	x	x		x	
Fasting Lipid Panel 	x			x		x	x 			
Adrenal Hormones Panel 	x		x		x		x 			
Mitotane level 	x 		x	x	x	x	x		x	
12-lead ECG 	x									
Mitotane therapy 		x	x	x	x	x	x			

Pembrolizumab infusion 			x	x	x	x	x			
Response assessment 	x	x 	Scans will be done every 12 weeks (+/-7 days) starting on C2D1							
Concomitant medications	x		x	x	x	x	x		x	
Adverse events	x		x	x	x	x	x		x	x
Optional Biopsy	x					x		x		

 Pregnancy test, serum or urine at baseline, urine or blood within 72 hours prior to every cycle for women of child-bearing potential; All WOCBP must have a negative serum or urine pregnancy test within 72 hours prior to start of study drug.

 Physical examination at screening and day 1 of each cycle (+/- 7 days). ECOG performance status must be documented within 10 days prior to each cycle and can be obtained remotely or in person.

 Hemoglobin, hematocrit, platelet count, RBC count, WBC count, percent and absolute differential count, sodium, potassium, chloride, bicarbonate, glucose, BUN, creatinine, calcium, total and direct bilirubin, total protein, albumin, ALT, AST, alkaline phosphatase, TSH, free T4.

 Fasting Lipid panel at screening, Cycle 2, Cycle 4, and Cycle 6. May be repeated with every other cycle per treating physician discretion.

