#### **5.2.4 Dose Modification and toxicity management for immune-related AEs associated with pembrolizumab and IO combination partners**

AEs associated with pembrolizumab or IO/IO combination exposure, may represent an immunologic etiology. These immune-related AEs (irAEs) may occur shortly after the first dose or several months after the last dose of pembrolizumab/combination treatment and may affect more than one body system simultaneously. Therefore, early recognition and initiation of treatment is critical to reduce complications. Based on existing clinical study data, most irAEs were reversible and could be managed with interruptions of pembrolizumab/combination treatment, administration of corticosteroids and/or other supportive care. For suspected irAEs, ensure adequate evaluation to confirm etiology or exclude other causes. Additional procedures or tests such as bronchoscopy, endoscopy, skin biopsy may be included as part of the evaluation. Dose modification and toxicity management guidelines for irAEs associated with pembrolizumab/combination treatment are provided in Table 6.

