## 7.0 STATISTICAL ANALYSIS PLAN

We will simultaneously monitor efficacy and toxicity using the Bayesian optimal phase 2 (BOP2) design (Zhou, Lee and Yuan, 2017). Specifically, let  $n$  denote the interim sample size, and  $N$  denote the maximum sample size. Let  $Y_{eff}$  and  $Y_{tox}$  denote the binary efficacy and toxicity endpoints, with  $Y_{eff} = 1$  and  $Y_{tox} = 1$  indicating that patients experience efficacy and toxicity, respectively. We assume that the joint distribution of  $(Y_{eff}, Y_{tox})$  follows a multinomial distribution with four elementary outcomes:  $(Y_{eff}, Y_{tox}) = (1, 1), (1, 0), (0, 1)$  and  $(0, 0)$ . Let  $\mathbf{p} = (P_{11}, P_{10}, P_{01}, P_{00})$  denote the probabilities of observing the four outcomes, and let  $p_{eff} = Pr(Y_{eff} = 1)$ ,  $p_{tox} = Pr(Y_{tox} = 1)$  and  $p_{eff,tox} = Pr(Y_{eff} = 1, Y_{tox} = 1)$ . When efficacy and toxicity endpoints are monitored separately, the joint distribution reduced to marginal distribution of efficacy and marginal distribution of toxicity, respectively. For trial monitoring and decisions, extreme toxicities (TOX) will be defined as any grade 3 or higher adverse event that is possibly, probably, or related to therapy received on this protocol. Any grade 3 or higher adverse event that is potentially treatable with steroids or hormonal replacement will only count as an extreme toxicity if it does not improve to grade 1 or better within 2 weeks of therapy.

The treatment is deemed unacceptable if  $p_{eff} \leq 0.23$  or  $p_{tox} > 0.5$ . Thus, we will stop enrolling patients and claim that the treatment is unacceptable if

$$Pr(p_{eff} > 0.23 | data) < \lambda \left( \frac{n}{N} \right)^\alpha,$$

or

$$Pr(p_{tox} \leq 0.5 | data) < \lambda \left( \frac{n}{N} \right)^{\alpha/3},$$

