where  $\lambda=0.5$  and  $\alpha=1$  are design parameters optimized to maximize the study power, i.e., probability of correctly concluding an efficacious and safe treatment as acceptable when  $p_{eff} = 0.3$ ,  $p_{tox} = 0.3$  and  $p_{efftox} = 0.18$ , while controlling that the probability of incorrectly claiming an inefficacious and toxic treatment, i.e., type I error, with  $p_{eff} = 0.23$ ,  $p_{tox} = 0.5$  and  $p_{efftox} = 0.15$ , to 9.5%. Note that in the safety stopping rule, the original publication of the design used the probability cutoff  $\lambda(n/N)^\alpha$ , here the attenuation factor 3 is added (i.e.,  $\alpha/3$ ) to obtain stricter interim stopping boundaries to enhance safety.

For the purposes of interim monitoring, toxicities and responses will be monitored for 24 weeks post start of the combination therapy.

This optimization is performed assuming a vague Dirichlet prior  $Dir(0.15, 0.08, 0.35, 0.42)$  for  $\mathbf{p}$ . The prior is chosen such that it corresponds to a prior effective sample size of 1 patient, and the prior estimates of  $p_{eff}$  and  $p_{tox}$  match the values specified when the treatment is unacceptable. The above decision rule leads to the following optimal stopping boundaries:

*Table 1: Optimized stopping boundaries*

# patients treated	Stop if # response <=	OR # toxicity	
		<=	>=
10	0	6	
20	3	11	
35	7	18	
50	11	25	

When the total number of patients reaches the maximum sample size of 50, we conclude that the treatment is acceptable if the number of responses are greater than 11, and the number of toxicities are less than 25; otherwise we conclude that the treatment is unacceptable. The go/no-go criteria in Table 1 are non-binding.

Below are the operating characteristics of the design based on 10000 simulations using the BOP2 web application (BOP2 V1.4.7.0), which is available at <http://www.trialdesign.org>.

*Table 2: Operating characteristics*

Scenario	Pr(Eff)	Pr(Tox)	Pr(Eff & Tox)	Early Stopping (%)	Claim Acceptable (%)	Average Sample Size
1	0.23	0.5	0.15	83.15	9.47	23.0
2	0.30	0.3	0.18	24.46	71.38	42.9

ORR will be summarized with a 95% confidence interval (Clopper-Pearson exact method).

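### The AE collection period is inconsistent across sections, and on the Section 6.2 reading the 24-week toxicity endpoint behind the stopping rule can be incomplete for patients who stop early

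*Combined protocol and SAP*

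**What the plan says.** Section 7.0 defines the toxicity outcome as "any grade 3 or higher adverse event that is possibly, probably, or related to therapy received on this protocol". Seriousness is not required. An event that steroids or hormone replacement could treat counts only if it has not improved to grade 1 or better within two weeks of therapy. For interim monitoring, "toxicities and responses will be monitored for 24 weeks post start of the combination therapy".

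Section 6.2 sets the reporting period: "All AEs from the time of intervention allocation/randomization through 30 days following cessation of study intervention must be reported by the investigator". For serious events the period runs "through 90 days following cessation of study intervention or 30 days following cessation of study intervention if the participant initiates new anticancer therapy", with the earlier date applying. Beyond those limits, "any SAE brought to the attention of an investigator at any time outside of the time period specified above must be reported immediately to Merck". That duty covers only events judged to be drug-related. The same section adds: "Investigators are not obligated to actively seek AEs or SAEs or other reportable safety events in former study participants".

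Three other places point to a longer period:
- Table 1 (Study Schedule of Activities) marks the row "Adverse events" in the Follow-Up column.
- Section 6.1.2.1 has AEs graded and recorded in follow-up as well as on study.
- Section 5.6 keeps participants who stop treatment early on the Section 2.2 schedule unless they withdraw.

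None of the three says how long AE collection lasts. Section 5.2.4 notes that immune-related events "may occur shortly after the first dose or several months after the last dose of pembrolizumab/combination treatment".

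**The concern.** The safety boundary compares a count of toxicities with the number of patients treated, so each patient's toxicity status over 24 weeks has to be known. On the Section 6.2 reading, a patient who stops treatment well before week 24 leaves the all-AE reporting period before the toxicity window closes. A related, non-serious grade 3 event in that interval can meet the Section 7.0 definition with no duty to report it. Serious events are better covered, but their limit falls from 90 to 30 days once new anticancer therapy starts, and the any-time rule depends on the event reaching the investigator.

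Two silences make this harder to resolve:
- Cessation of study intervention is not defined for a patient who stops pembrolizumab and stays on mitotane.
- Section 7.0 does not say how a patient with less than 24 weeks of toxicity follow-up enters a look.

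Any shortfall in the count acts in one direction: it makes the safety boundary harder to reach.

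**Working it through.** **1. The plan's own figures.** Section 7.0 gives λ = 0.5, α = 1, the prior Dir(0.15, 0.08, 0.35, 0.42), limits of 0.23 and 0.5, and looks at 10, 20, 35 and 50 patients. The marginal priors are:
- p_eff ~ Beta(0.15 + 0.08, 0.35 + 0.42) = Beta(0.23, 0.77)
- p_tox ~ Beta(0.15 + 0.35, 0.08 + 0.42) = Beta(0.5, 0.5)

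The rule stops for toxicity when Pr(p_tox ≤ 0.5 | data) falls below 0.5(n/50)^(1/3). At n = 10 the cutoff is 0.292; the posterior probability is 0.500 with 5 toxicities and 0.265 with 6, so the boundary is 6. All eight boundaries reproduce: responses ≤ 0/3/7/11 and toxicities ≥ 6/11/18/25. The last one is a tie, because 25 of 50 gives exactly 0.5; the plan's table treats it as a stop.

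An exact recursion over the joint response and toxicity counts gives:

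| Scenario | | Early stop | Accepted | Average N |
|---|---|---|---|---|
| 1 (0.23, 0.5, 0.15) | Stated | 83.15% | 9.47% | 23.0 |
| | Recomputed | 83.40% | 9.56% | 22.96 |
| 2 (0.30, 0.3, 0.18) | Stated | 24.46% | 71.38% | 42.9 |
| | Recomputed | 23.79% | 71.91% | 43.1 |

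The 9.47% against 9.56% is within simulation error: √(0.0947 × 0.9053 / 10000) is about 0.29 points.

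**2. The gap under Section 6.2 alone.** Pembrolizumab is given every 6 weeks (Section 5.2.3), so doses at weeks 0, 6, 12 and 18 precede week 24. With w the week of the last dose, and the clock started at that dose:
- non-serious gap = 24 − (w + 30/7)
- serious gap without new therapy = max(0, 24 − (w + 90/7))

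| Last dose (week) | All-AE duty ends (week) | Non-serious gap (weeks) | Serious gap, no new therapy (weeks) |
|---|---|---|---|
| 0 | 4.3 | 19.7 | 11.1 |
| 6 | 10.3 | 13.7 | 5.1 |
| 12 | 16.3 | 7.7 | 0 |
| 18 | 22.3 | 1.7 | 0 |

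If new anticancer therapy starts, the serious limit can be as short as 30 days and the serious gap then equals the non-serious one. If the clock starts at a later stop date, or when mitotane stops, every gap is shorter.

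**3. How many patients could have any gap.** There is no gap if the clock starts on or after day 168 − 30 = 138. As an illustration, assume that treatment stops at progression, that progression times are exponential, and that the median is the 4.1 months Section 4.1 gives for mitotane alone. Then 1 − 2^(−(138/30.4375)/4.1) = 53.5%. This is the share of patients with any gap, even one day. It is not the share of toxicities missed.

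**4. What an undercount would do.** The documents give no missed share, so assume that a fraction m of toxicities goes uncounted, independently of response. The observed rates become p_tox(1 − m) and p_efftox(1 − m). At the null rates (0.23, 0.5, 0.15):

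| m | Observed p_tox | Accepted |
|---|---|---|
| 0 | 0.500 | 9.6% |
| 5% | 0.475 | 13.9% |
| 10% | 0.450 | 18.6% |
| 20% | 0.400 | 27.4% |

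If instead the loss falls only on non-responders, with 10% or 20% of their toxicities missed, acceptance is 15.0% or 21.0%.

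**The case against.** The strongest reply is that AE collection does not in fact stop at 30 days. The Follow-Up mark in Table 1 and Sections 6.1.2.1 and 5.6 all extend it, and a patient in follow-up is not clearly a former participant. This stands. A reader might infer that there is an established unobserved window; the documents support only a contradiction, one side of which would create it. The reply does not settle the matter, because those places give no duration. The AE-specific visits in Sections 6.1.7.3.1 and 6.1.7.3.4 fall at about 30 days, and the Section 6.1.7.3.3 contacts are for survival status.

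A reader might also infer that early stoppers are counted as free of toxicity. No section says so; Section 7.0 is silent.

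Third, mitotane is listed in Table 5 as a trial intervention and may continue, so cessation may come later than the last pembrolizumab dose. This stands as an ambiguity. On the other side, Appendix 5 equates study intervention with the Merck product for AE purposes, and Table 5 labels mitotane standard of care.

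Fourth, 53.5% overstates the harm. On the Table 1 and Table 3 scan schedule (weeks 6 and 18), the same curve has about 21% progressed by week 6 and 50% by week 18. A patient stopped at week 18, with the clock started there, has a gap of only 1.7 weeks. Continued treatment pending confirmation of progression shortens gaps further, and a patient already counted as a toxicity cannot be undercounted later. These points stand, so the figure should not be read as a measure of bias.

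Last, the go/no-go criteria are non-binding. Whoever exercises that judgement still needs complete counts.

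**Conclusion.** The point holds as an inconsistency that should be resolved. Section 7.0 needs 24 weeks of toxicity information, Section 6.2 does not require it for patients who stop early, and other sections imply longer recording without a duration. On the Section 6.2 reading with the clock at the last pembrolizumab dose, between 1.7 and 19.7 weeks of the window carry no duty to report non-serious events. On other readings the gap is smaller or absent.

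The effect on the design cannot be fixed from the documents. The rise from 9.6% to between 13.9% and 27.4% rests on assumed missed shares of 5% to 20% and on missed events simply not entering the count. It shows that the rule is sensitive to modest under-capture, not that under-capture of that size will occur. With full 24-week capture the stated operating characteristics stand.

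**What to change.** - In Section 6.2, require collection of grade 3 or higher AEs, with relatedness, through the later of 30 days after cessation and 24 weeks after C1D1, whatever the treatment status. Flag events that follow new anticancer therapy.
- Bring Table 1 (Schedule of Activities), Section 6.1.2.1 and Section 7.0 into line with that period. Use the existing follow-up contacts, with one timed at or after week 24.
- Define which drug's stop is the cessation that starts the reporting clock.
- In Section 7.0, state how a patient with incomplete 24-week toxicity follow-up is counted at each look.
- Leave Table 9 unchanged. It governs expedited reporting of serious events, pregnancy or lactation exposure and events of clinical interest; adding non-serious events there would put them on that clock.

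The cost is protocol wording, a few AE questions at contacts largely scheduled already, and harder attribution of events after new therapy. The boundaries and sample size do not change.
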